## **➤ At 1 Year and 2 Year Follow up**

### **1- Since your surgery does your abdomen seems:**

- firm
- not firm

### **2- Do you have a new hernia or bulge?**

- No
- yes (if so Operated side; Scar region; other side; both side, elsewhere (specify))

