One hundred patients will be followed using the online database for registration and patient outcome measurements, including pre-operative, operative, discharge, post-operative course (D1 and D8 follow up), 1 month (D30 follow up), 1 Year and 2 Year follow up. The pain nurses will carry out the pain evaluation on the day of surgery (D0) and on postoperative day 1 (D1) (by phone call in case of day surgery). Pain on day 8 is assessed either during clinical exam or by phone if the patient is already discharged. Patients will be given an appointment for a clinical visit on day 30 (D30 follow up). The post-operative visit at 1 month (D30 follow up) is the standard of care for patient follow up following primary abdominal wall and incisional hernia surgeries.

For long-term follow up, two sets of self-administered QOL questionnaires will be administered by phone call at 1 Year and 2 Year follow-up.

Follow up by phone questionnaires will be performed by a Clinical Research Associate mandated by Club Hernie, independent from the operative surgeons

The Clinical Research Associate will enter into the database answers from the patient-based self-assessment questionnaires.

The answers will be registered without any medical adjustment into the database. The patients who complain of any trouble will be invited to have a clinical visit at the surgeon's office. The correlation between the patient's answer and clinical assessment and physical examination will then be determined.

A patient will be considered lost to follow-up after 5 failed attempts of meticulous postal reminders and phone calls at various times, therefore minimizing the non-response bias.

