### **5.8 2 year follow-up**

- QoL and patient satisfaction Questionnaire (Appendix C)
- Post-operative complications (including SAEs)
- Pain assessment measured with VAS score\*

Follow-up at 2 year: All patients will be contacted by phone in order to complete a self-assessment questionnaire.

\*Patients who complain of any trouble will be invited to have a clinical visit at the surgeon's office. Post-operative complications and VAS score will be recorded.

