### **Statistical Analysis Plan Summary**

The analysis will be performed for primary and secondary endpoints, all data will be analyzed, according to the methods previously described in the general considerations section.

- 1) Descriptive Analysis of patients registration and outcomes measurement
- 2) Baseline and Demographic Data Analysis
- 3) Operative Data Analysis
- 4) Primary endpoints measured within 1month, 1 Year and 2 Year follow-up
  - a. Peri-operative complications
  - b. Post-operative complications such as anticipated device related complications as pain, recurrence, complications related to adhesions, wound complications, other postoperative complications, SAEs...
  - c. All complications
- 5) Secondary endpoints analysis during the whole follow-up
  - a. Surgical technique and mesh fixation
  - b. Operative time descriptive analysis
  - c. Ease of use / mesh manipulability assessment by surgeons
  - d. Length of hospital stay analysis
  - e. Quality of life and patient satisfaction analysis
  - f. Surgeon satisfaction

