**9- Have you had a re-operation on your abdominal wall?**

- No
- Yes (if so please specify)

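### The 1- and 2-year questionnaire asks about a present hernia and an undated, unattributed re-operation, so by itself it does not measure cumulative recurrence

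*Protocol*

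**What the plan says.** Section 1.1 of the Protocol makes the incidence of complications, recurrence among them, the primary objective. Section 6.2 repeats this. It lists "Post-operative complications such as anticipated device related complications as pain, recurrence, complications related to adhesions" and gives the reporting times as "Primary endpoints measured within 1month, 1 Year and 2 Year follow-up".

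After the 1-month visit, the scheduled contacts are two telephone calls (sections 2.2, 5.7 and 5.8). Both use one item set, headed "At 1 Year and 2 Year Follow up" in Appendix C. Three features matter here:

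- Item 2 asks "Do you have a new hernia or bulge", with location options if the answer is yes.
- Item 9 asks "Have you had a re-operation on your abdominal wall", answered no or "Yes (if so please specify".
- Item 10 asks for a verdict on the hernia operation without saying which one, if there has been more than one.

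Under section 2.2, a Clinical Research Associate independent of the surgeons makes the calls, and "The answers will be registered without any medical adjustment into the database". Sections 5.7 and 5.8 also list "Post-operative complications (including SAEs") as an entry separate from the questionnaire. An asterisked note in each section says that patients with a complaint are offered a visit to the surgeon, and that complications and the pain score are then recorded.

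**The concern.** An incidence by 1 or 2 years needs either a question of the form 'at any time since' or a date for each event. Item 2 has neither. Suppose a hernia recurs at month 5 and is repaired at month 8. At both calls the patient can truthfully say that there is no hernia now. If the second repair went well there may be no complaint, and so no reason for the visit mentioned in the note.

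Item 9 does pick up this patient, but it covers any abdominal-wall re-operation. Unless the patient volunteers the reason, a repair of a recurrence cannot be told from surgery for infection, removal of the mesh, or an operation elsewhere on the wall.

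The recurrences exposed to this are those serious enough to be operated on. Recurrence is also the rate on which section 6.1 sizes the registry, and so few events are expected that each one matters.

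**Working it through.** **1. The plan's own figure.** Section 6.1 gives a recurrence rate p = 5.9%, a 95% confidence interval and a precision d = 5 percentage points. The usual normal-approximation formula is n = z² p(1 − p) / d², with z = 1.96:

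n = 3.8415 × 0.059 × 0.941 / 0.0025 = 85.3, rounded up to 86.

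This reproduces the stated 86. This point does not change the sample size.

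**2. Expected events.** 0.059 × 86 = 5.07, so about 5 recurrences.

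**3. What each item records for a recurrence repaired before the call.**

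| Item | Time frame asked | Answer | What stays unknown |
|---|---|---|---|
| 2 | Now | No | That a recurrence occurred |
| 9 | Open-ended | Yes | Date, reason and mesh status, unless volunteered in free text |

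Item 1 of the same form is framed as since the surgery. Interval wording was therefore available but was not used in items 2 and 9.

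**4. Timing.** For a patient reached at both calls, linking the two records helps: no at 1 year and yes at 2 years places the re-operation between the calls. For a patient missed at 1 year and reached at 2 years there is no such bracket, and without a date the event cannot be assigned to the first or second year. The protocol does not say whether a patient missed at 1 year is called again at 2 years; if so, this is where timing is least certain.

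**5. Worst case, item 2 read alone.** The share of recurrences repaired before the call is not in the document, so it is shown as a range. Intervals are exact (Clopper-Pearson) at N = 86.

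| Repaired, of 5 (assumed) | Item 2 shows | Rate | 95% CI |
|---|---|---|---|
| 0 | 5/86 | 5.8% | 1.9 to 13.0% |
| 1 | 4/86 | 4.7% | 1.3 to 11.5% |
| 2 | 3/86 | 3.5% | 0.7 to 9.9% |
| 3 | 2/86 | 2.3% | 0.3 to 8.1% |

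Each repaired recurrence that item 2 does not show lowers the estimate by 1/86, about 1.2 percentage points. If item 9 is also used and its free text names recurrence as the reason, the count stays at 5/86.

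**The case against.** The best reply is that the form should be read as a whole. Item 2 covers the hernia present now and item 9 covers past re-operation, so the patient repaired at month 8 is flagged at both calls, and the open prompt invites a reason. This stands. The event is not lost from the form; what is missing is reliable attribution and dating.

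A second reply is that nothing in the protocol says recurrence is counted from item 2. Complications are a separate entry at 1 and 2 years, and section 6.2 places recurrence among them. This also stands in part. However, the note in sections 5.7 and 5.8 mentions recording in connection with a visit for patients who complain, and section 2.3 rules out source data verification. The document does not show how a repair done between calls, in a patient who now feels well, would reach that entry. Nor does it show that it would fail to.

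Two stronger readings are tempting, and the text supports neither.

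- A reader might infer that one re-operation will be double-counted because item 9 reads yes at both calls. That would need the 1- and 2-year windows to be separate intervals, added together without linking a patient's records. The protocol says neither. If the reporting times are cumulative, a month-8 event properly belongs in both figures.
- A reader might infer that good results of a second repair will be credited to the study mesh. Answers after a re-operation can indeed describe the later repair, but no passage says how they are analysed. That rule can sit in the statistical analysis plan, which is not shown. Reporting all patients regardless of re-operation is also a legitimate descriptive choice.

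Finally, an analysis plan can define how to count. It cannot recover a date, reason or mesh status that was never asked for.

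**Conclusion.** The point holds as a weakness in the data collected. The 1- and 2-year form neither asks about recurrence cumulatively nor dates and attributes re-operations, so on its own it cannot give recurrence by 1 and 2 years as the primary objective requires. How far the final estimate is affected depends on what patients volunteer at item 9 and on how complete the separate complications entry is. The document settles neither.

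The fall from 5.8% to between 4.7% and 2.3% is a worst case for item 2 alone, with one to three of five recurrences assumed repaired. It is not a forecast of bias in the reported endpoint. The change is worth making because it costs little and the information is hard to recover later.

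**What to change.** - **Item 2.** Reword to: *Since your operation (or since our last completed call), have you had a hernia or bulge at the repaired site, even if it has since been treated?* Keep a follow-on location question so that a hernia elsewhere is still recorded.
- **Item 9.** Give it the same reference period, and prompt for the approximate date, the reason, and whether the mesh was removed or another placed.
- **Counting.** Count recurrence once per patient and cumulatively, as the first of a yes at item 2 or a re-operation for recurrence. Flag pain, quality-of-life and satisfaction answers given after a re-operation. If the statistical analysis plan already has such rules, the new fields supply the data they need.

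The cost is two reworded telephone items and a few sub-fields, with no additional contact and no change to the sample size. The downside is a slight recall burden: about a year for a patient reached at both calls, and up to about two years for one missed at 1 year. An approximate date is enough.

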### **1.1 Primary Objective**

Evaluate the incidence of peri-operative and post-operative complications, with post-operative evaluations occurring, at discharge , 1 week (D1 and D8 follow up), 1 month (D30 follow up), 1 Year and 2 Year follow up after primary and incisional abdominal wall hernia surgeries using Symbotex™ Composite Mesh by open or laparoscopic approach (such as anticipated device related complications such as pain, recurrence, complications related to adhesions, wound complications, other postoperative complications, SAE...).

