### **2.2 Scope**

One hundred consecutive adult patients scheduled for primary and incisional abdominal wall hernia surgeries using Symbotex™ Composite Mesh will be reported in the Club Hernie database in real time.

A working group of hernia surgeons, under the auspices of the Club Hernie Society board, have created a French Registry of Abdominal Wall Hernias called Club Hernie. The Club Hernie is a non-profit organization created in 2009, currently including 30 French surgeons' members, with the aim to improve the healthcare treatments in parietal surgery by an assessment of surgical practices, promoting research in abdominal wall surgery using an internet database open to surgeon members to monitor their own hernia practice and outcomes.

This online database consists of a systematic and consecutive data entry of all patients treated for Inguinal Hernia and Ventral Hernia by the 30 French surgeon members, with standard data captured of all preoperative, perioperative and post-operative data.

Covidien is contracting with Club Hernie to act as a authorized representative to perform sponsor's clinical study-related duties and functions, such as implementation and conduct of this observational registry study.

The Club Hernie database will be used for the 100 patient registry from the Club Hernie surgeon members using Symbotex™ Composite Mesh. The Club Hernie database is free for use by surgeons. Only Hernia Club surgeon members are allowed to get an account for the database, protected by identifier and password. The surgeon members having signed the Quality Charter are committed to respecting its principles Club Hernie surgeon members participating in the study will be surgeon members using Symbotex™ Composite Mesh for primary abdominal wall and incisional hernia surgeries according to their current therapeutic practice.

The database is required to be completed anonymously. Therefore, it does not contain any patient data such as name, date of birth, social security number or address of the patient.

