#### **4.1 Inclusion Criteria**

- All patients regardless of gender  $\geq 18$  years of age presenting with ventral hernias.
- Patients will be informed by surgeon with a written information notice of the nature of the observational registry study.

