#### POSSIBLE COMPLICATIONS

The possible complications associated with the use of Symbotex™ composite mesh are those typically associated with surgically implantable mesh: seroma, hematoma, recurrence, adhesions, fistula formation, infection, inflammation, chronic pain, and/or allergic reactions to the components of the product.

Potential events associated with state of the art mesh with similar indication may include: organ injury (including bowel and visceral injury), trocar-site herniation, bowel obstruction and urinary retention (related with the use of anesthetics).

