### **4- Where are these symptoms located?**

- Several possible answers:
- Operated side
- Scar region
- Other side
- Both sides
- Elsewhere (specify)

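### The 1- and 2-year hernia-or-bulge item has no location option for the repaired site, so on its own it does not reliably separate recurrence from trocar-site or other new hernia

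*Protocol*

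**What the plan says.** The study population is adults "years of age presenting with ventral hernias" (section 4.1), operated "by open or laparoscopic approach" (section 1.1). Recurrence is a named component of the primary endpoint (sections 1.1 and 6.2) and the quantity on which the sample size is based (section 6.1).

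At 1 and 2 years every patient is contacted by phone for a self-assessment (sections 5.7 and 5.8). Item 2 of that questionnaire in Appendix C asks "Do you have a new hernia or bulge" and offers, for a positive answer, "yes (if so Operated side; Scar region; other side; both side, elsewhere (specify". The same side-based list follows "Where are these symptoms located" (item 4 at 1 and 2 years, item 2 at D30).

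Section 2.2 states: "The answers will be registered without any medical adjustment into the database". It then provides that patients reporting trouble are invited to the surgeon's office and that their answers are compared with the physical examination. Surgical approach, hernia type and hernia location are recorded at operation (section 5.2). Item 9 of the long-term questionnaire asks about re-operation, with room for detail.

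The instructions for use in Appendix B list recurrence among the complications typical of mesh. In a separate sentence they list "organ injury (including bowel and visceral injury), trocar-site herniation, bowel obstruction and urinary retention".

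**The concern.** The options describe a hernia that has a side. Many ventral hernias lie in the midline, where operated side, other side and both sides have no clear meaning. The list lacks the one location that defines recurrence, the place that was repaired. The nearest substitute, the scar option, changes meaning with the approach. After open repair the scar usually overlies the repair. After laparoscopy the visible scars may be trocar scars away from it.

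The answer list is fixed in the protocol, so this is not a detail left to a later analysis plan. An analysis plan can say how to combine sources, but it cannot recover a location that the form did not capture. Recurrence is expected to be rare here, so a few answers placed in the wrong category would visibly change the reported rate.

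**Working it through.** **Step 1. How plausible events would be recorded.** These are readings of the answer list, not observed answers.

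| Event | Likely option | Is it recurrence? |
|---|---|---|
| A. Open midline repair, hernia returns under the scar | Scar region | Yes |
| B. Laparoscopic umbilical repair, hernia returns at the umbilicus away from the trocar scars | No natural option: operated side or elsewhere | Yes |
| C. Laparoscopic repair intact, hernia at a trocar site | Scar region | No |
| D. New groin hernia after either approach | Other side or elsewhere | No |

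No single option corresponds to recurrence. Taking the scar option as recurrence would include C and miss B. Taking every positive answer would include C and D. The protocol states neither rule; they are used here only to test what the codes can carry.

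**Step 2. What else is recorded.**

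- Operative data give the original site and the approach. They do not give the site of the new bulge, so they help to interpret an answer but do not settle B or C.
- Free text is attached only to the last option. It helps in B and D if that option is chosen, and not in C if the scar option is chosen.
- The re-operation item helps only for patients already re-operated.
- The clinical visit can settle all four cases, for patients who accept the invitation.

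The gap is therefore patients who report a bulge and are not examined.

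**Step 3. The plan's own figure.** Inputs from section 6.1: rate p = 0.059, precision d = 0.05, two-sided 95% confidence.

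n = 1.96² × p(1 − p) / d² = 3.8415 × 0.059 × 0.941 / 0.0025 = 85.31, rounded up to 86. The stated 86 is reproduced.

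**Step 4. Size of one misplaced answer.** With 100 recruited and 15% lost, 100 × 0.85 = 85 patients are evaluable. Expected recurrences are 0.059 × 85 = 5.0. One answer moves the rate by 1/85 = 1.18 percentage points, which is 1/5 = 20% of its expected value.

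**Step 5. Illustration with assumed counts.** The documents give no frequency for trocar-site or groin hernia, or for non-attendance at the visit. Exact (Clopper-Pearson) 95% intervals:

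| Counted as recurrence | Rate | 95% CI |
|---|---|---|
| 3/85 (two true recurrences not counted) | 3.5% | 0.7 to 10.0% |
| 5/85 (all correct) | 5.9% | 1.9 to 13.2% |
| 7/85 (two other hernias counted) | 8.2% | 3.4 to 16.2% |

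Two answers in either direction shift the rate by 2 × 1.18 = 2.4 points, less than the planned precision of 5 points. The first and last rows come from different hypothetical counting rules and would not both apply to one analysis.

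**The case against.** The strongest reply is that item 2 is nowhere said to be the recurrence endpoint. Sections 5.7 and 5.8 list post-operative complications separately from the questionnaire. Section 6.2 places recurrence under the primary endpoint and the questionnaire under the secondary endpoints. Deriving recurrence from several sources commonly belongs in the analysis plan, and its absence from the protocol is no fault. Keeping the patient's answer unadjusted preserves the raw response and does not bar classification by examination. A trained interviewer asks the questions, and off-midline ventral hernias do have a side.

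All of this stands. It limits the point to unexamined patients, for whom the questionnaire is the only scheduled source at 1 and 2 years.

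Three stronger readings are tempting, and the documents do not support them:

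- *Recurrence cannot be told apart from other hernia at all.* The free-text option, the operative record, the re-operation item and above all the examination can separate many cases.
- *The error runs in opposite directions for open and laparoscopic repair.* In the cases above, both the missed and the false recurrence (B and C) are laparoscopic, and the open case (A) is coded correctly. Section 6.2 also names no recurrence analysis by approach.
- *The list was taken over from an inguinal form.* The host database covers "systematic and consecutive data entry of all patients treated for Inguinal Hernia and Ventral Hernia", which makes this conceivable, but the protocol does not say so.

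**Conclusion.** The point holds in a limited form. The location options fit midline ventral hernia poorly and omit the repaired site, so item 2 alone does not reliably separate recurrence from trocar-site or other new hernia. The weakness matters for patients who report a bulge and do not attend the invited visit.

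Each misclassified answer is worth about 1.2 points on an expected 5.9%, assuming 85 evaluable patients and the plan's own rate. The total effect cannot be stated, because neither the number of such answers nor attendance at the visit is given. This is a matter of instrument wording, of minor to moderate weight, and cheap to correct.

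**What to change.** Replace the location options of item 2 at 1 and 2 years with:

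- *at the place where the hernia was repaired*
- *at another surgical scar (including trocar scars)*
- *in the groin*
- *elsewhere (specify)*

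Use the same list in the symptom-location items (D30 item 2; 1- and 2-year item 4).

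Pair this with a short reporting rule. Where an examination took place, classify recurrence by the examination. For unexamined patients, report a bulge at the repaired place as patient-reported recurrence, and bulges at another scar or trocar site separately. The new list still relies on patients locating the bulge themselves, so the two levels of evidence should be shown apart.

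The cost is a change to one answer list on the phone form and in the database, with no added visit or question. The downside is that the new codes do not match entries already stored with the older list, including other patients' entries if the registry shares the form.

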### **3- Do you currently feel any post-operative discomfort?**

- No
- Discomfort
- “Pins and needles”
- Loss of sensation
- Moderate pain
- Severe pain
- Other symptoms (please specify)

### **4- Where are these symptoms located?**

- Several possible answers:
- Operated side
- Scar region
- Other side
- Both sides
- Elsewhere (specify)

### **5- When exactly do you feel these symptoms?**

- Several possible answers:
- During lifting, coughing or pushing
- During others types of effort (please specify)
- After physical effort or and the end of the day
- At any other particular time (please specify)

-At any time

